### **8.2.6 Safety and adverse effects of treatment:**

Evaluate safety and adverse effects of the treatment by CTCAE 4.0 toxicity scale.

### **8.2.7 Comparison of Ki-67 expression changes between subjects and a historical cohort**

The reason a historic cohort will be studied is to provide the context in which to assess the effects of exemestane in reducing Ki-67 from baseline to post-exposure to exemestane. Specifically, there may be a change in Ki-67 expression from pretreatment biopsy to final surgical specimen in the historical control cohort suggesting that time alone (between biopsy and surgery) or potentially differences in tissues

acquisition (biopsy versus surgical specimen) may have an impact on Ki-67 expression.

The study participants will be matched with a historical nonrandomized control group based on age (+/- 5 years), disease type and BMI (>20-24, 25-30, > 30). This control group will provide a reference for how Ki-67 may change based on time (specifically time between biopsy and surgery which has to be within 42 days) or differences in specimen collection (endometrial biopsies versus surgical specimen), independent of exemestane exposure.

#### **8.2.8 Evaluation of the levels of exemestane in the plasma samples pre and post treatment**

Comparison of pharmacokinetic (PK) levels of plasma exemestane pre-and post treatment will be analyzed at Cancer Pharmacology Laboratory (CP Laboratory) at University of Wisconsin Carbone Cancer Center (UWCCC). The plasma samples collected during the baseline (pre-surgical) clinic visit and before surgery will be processed as mentioned in section 10.2.4 at each participating center and batch shipped to CP Laboratory for analysis.

#### **8.3 Off-Agent Criteria**

Participants may stop taking exemestane for the following reasons: completed the protocol-prescribed intervention, AE or serious adverse event (SAE), noncompliance, contraindicated medications, medical contraindication or surgery is not performed within 21 to 42 days of the first dose of exemestane. Any participant discontinuing exemestane prior to 1 day before surgery will be instructed to bring the exemestane bottles and the completed pill diary to her next appointment. A final study visit will occur at the participant's first post-surgical visit.

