### **7.7 Follow-up Contact**

The final study visit will coincide with the day of surgery unless there are any unresolved AEs (with a possible, probable or definite attribution to the study agent) on the day of surgery. The unresolved AEs will be assessed via telephone call during the postoperative period, before or on the day of the 1st post-surgical follow-up visit. AEs that occurred after surgery will not be recorded.

**For EOG site only**, follow-up at the standard of care post-operative visit will be performed in order to collect long-term safety information of the study treatment, whether or not the participant has any ongoing adverse events at the surgery visit.

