#### **8.4 Off-Study Criteria**

Participants may go 'off-study' for the following reasons: surgery and the final study visit has occurred, AE/SAE, lost to follow-up, non-compliance, contraindicated medication, medical contraindication, withdrawal of consent, death, determination of ineligibility (including screen failure).

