## **13. STATISTICAL CONSIDERATIONS**

### **13.1 Study Design/Description**

This is a multi-center, phase IIA, single-arm ‘window of opportunity’ pilot study of 25 mg per day exemestane for 21 to 42 days in patients undergoing planned surgery for CAH/EIN or low grade endometrial cancer, with an age, disease and BMI-matched comparator cohort, obtained from each institution’s biobank,

We plan to enroll up to 40 patients over 12-18 months at an accrual rate of 2-3 patients per month. Although all subjects will have CAH/EIN or low grade endometrial cancer based on their referral biopsy, we anticipate that some subjects will not have CAH/EIN or low grade endometrial cancer on central pathology review, thus making them ineligible for final analysis. Additionally, tissue samples may not be adequate for measuring Ki-67 expression. We therefore anticipate that approximately 25% of subjects will not be eligible for final analysis. This will result in 30 evaluable patients, the effective sample size for the study.

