### 13.4 Primary Objective, Endpoint(s), Analysis Plan

The primary objective is to determine if there is a decrease in proliferation index, measured by percent Ki-67 expression, in CAH/EIN or low grade endometrial cancer cells from baseline to post-exposure. Therefore, the primary endpoint is the absolute change in Ki-67 expression in endometrial cancer cells from baseline to post-exposure. We will evaluate the change from baseline to post-exposure in absolute change in Ki-67 using one-sample Student's t-test or Wilcoxon signed-rank test, as appropriate. In addition, we will evaluate the change relative to the change recorded in the historic cohort.

Ki-67 values for patients with endometrial cancer are available in prior research. When the patients from this paper are limited to those with low grade cancers, the mean (standard deviation) of the decrease from baseline was 7.2 (7.5) among the treated patients. Given an SD of 7.5, the table below shows the detectable effect sizes (defined as the mean change divided by the standard deviation of the change) and mean changes for a one-sided test for significance level  $\alpha=0.05$  and various power ( $1-\beta$ ) levels for the primary endpoint given the effective sample size of 30. For example, using an 0.05 level one-sided one-sample Student t-test, we would be able to detect an effect size of 0.50, which corresponds to a mean decrease of 3.8, with 0.85 power.

	Power		
	0.80	0.85	0.90
Effect Size	0.46	0.50	0.55
Mean Decrease	3.5	3.8	4.1

The mean decreases in this table are smaller than the mean difference in the treatment group for those with low grade endometrial cancer in the prior research with letrozole. We are including CAH/EIN in addition to low grade endometrial cancer in the current study and therefore it is not unreasonable to expect a lesser treatment effect for these patients with a less severe form of the disease. For these reasons, we feel there is a need to power for smaller differences.

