### 13.6 Reporting and Exclusions

As noted above, we anticipate that approximately 25% of patients will not have CAH/EIN or low grade endometrial carcinoma on central pathology review or their tissue samples will not be adequate for measuring Ki-67 expression, thus making them unevaluable for final analysis. This will result in 30 evaluable patients, the effective sample size for the study. These cases will be considered random loss, and will be excluded from analysis. Otherwise, all cases will be included in the analysis regardless of

compliance with the protocol treatment. All cases that received any amount of exemestane will be included in the analysis of toxicity as indicated below.

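### The off-agent and off-study rules do not secure post-treatment specimens from women who stop exemestane early, although the primary analysis is meant to include all cases regardless of compliance

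*Combined protocol and SAP*

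**What the plan says.** **Stopping the agent (8.3).** Adverse events, noncompliance, contraindicated medication and medical contraindication are among the reasons to stop exemestane. A woman who stops before the day preceding surgery brings her bottles and diary to her next appointment, and then: "A final study visit will occur at the participant's first post-surgical visit". Specimens are not mentioned.

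**Leaving the study (8.4).** The permitted reasons include "surgery and the final study visit has occurred, AE/SAE, lost to follow-up, non-compliance, contraindicated medication", followed by medical contraindication, withdrawal of consent and others. Completion of surgery and the final visit is one item. The tolerability and adherence reasons are separate items, so they can apply before surgery.

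**Final visit (7.6, 7.7).** Section 7.6 makes the day of surgery the final study visit. It lists estradiol, progesterone, the plasma exemestane sample and tampon removal before the operation, and 10.2.4 repeats that timing for the plasma sample. Section 7.7 agrees: "The final study visit will coincide with the day of surgery unless there are any unresolved AEs" attributed to the agent.

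**Specimens.** The Schema promises research-biopsy and surgical tissue for each enrolled participant. Section 10.1.1 takes the post-treatment paraffin block from standard-of-care pathology.

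**Analysis set (13.6).** Women who fail central pathology review or have inadequate tissue are excluded. "Otherwise, all cases will be included in the analysis regardless of" compliance with protocol treatment. Section 5.7 defines a secondary per-protocol set at 80% or more of doses.

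**The concern.** The reasons for stopping the drug and for leaving the study largely overlap, so the text does not separate ending treatment from ending follow-up. A site that takes a woman off study for an adverse event two weeks into dosing, and books her final visit after surgery as 8.3 says, has no instruction to draw her pre-surgery blood, collect her tampon or send her surgical block. Early stopping is foreseen: 5.6 provides for permanent discontinuation after defined related events.

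Women lost this way would be those with poor tolerability or adherence, and they plausibly have a smaller Ki-67 change. Leaving them out would tilt the estimate towards the drug in an analysis described as covering all cases. The 25% allowance in 13.1 and 13.6 covers only pathology review and tissue adequacy, so such losses would be additional. Estradiol, progesterone, plasma exemestane and tampon markers are secondary endpoints, but they are the more exposed data, because a visit after hysterectomy cannot replace samples due before it.

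**Working it through.** **1. The plan's own figure.** Section 13.4 gives "Given an SD of 7.5", an effective sample of 30 and, "using an 0.05 level one-sided one-sample Student t-test", states that "we would be able to detect an effect size of 0.50, which corresponds to a mean decrease of 3.8, with 0.85 power". Enrolment in 13.1: "We plan to enroll up to 40 patients over 12-18 months"; 40 × (1 − 0.25) = 30.

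Power = P(T > t(0.95, n−1)), where T is noncentral t with n−1 degrees of freedom and noncentrality √n × (mean decrease / 7.5).

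| n = 30, power | Effect size | Mean decrease | Plan |
|---|---|---|---|
| 0.80 | 0.465 | 3.49 | 0.46 / 3.5 |
| 0.85 | 0.501 | 3.76 | 0.50 / 3.8 |
| 0.90 | 0.547 | 4.10 | 0.55 / 4.1 |

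The plan's table reproduces.

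**2. What the text leaves open for an early stopper who has the planned hysterectomy.**

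| Item | Text for collection | Text that leaves it open |
|---|---|---|
| Surgical block (Ki-67) | Schema: each enrolled participant; 10.1.1: standard-of-care block | 8.4: may be off study before surgery; no instruction after that |
| Estradiol, progesterone, plasma exemestane, tampon | 7.6 and 10.2.4: before surgery | 8.3: final visit after surgery; 8.4 as above |
| Place in primary analysis | 13.6: regardless of compliance | No Ki-67 change exists if the block is not sent |

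The block remains obtainable after any hysterectomy. The pre-surgery samples do not.

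**3. Illustrative bias.** Let f be the share who stop early and are lost, and r their effect as a fraction of that in women who stay on agent. The documents give neither for this trial. Take the mean decrease in women who stay on agent as 3.8.

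All-treated mean = 3.8 × (1 − f) + 3.8 × r × f; overstatement = 3.8 / all-treated mean − 1.

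| f | r = 0 | r = 0.5 |
|---|---|---|
| 5% | 3.61; 5.3% | 3.71; 2.6% |
| 10% | 3.42; 11.1% | 3.61; 5.3% |
| 20% | 3.04; 25.0% | 3.42; 11.1% |

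In points, the overstatement at f = 10% is 3.8 − 3.61 = 0.19 to 3.8 − 3.42 = 0.38.

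**4. Does retention recover power?** Same formula, SD held at 7.5, r = 0.

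| Handling | n | Mean | Power |
|---|---|---|---|
| Nobody stops | 30 | 3.80 | 0.856 |
| 10% stop and are dropped | 27 | 3.80 | 0.821 |
| 10% stop and are kept | 30 | 3.42 | 0.786 |
| 20% stop and are dropped | 24 | 3.80 | 0.777 |
| 20% stop and are kept | 30 | 3.04 | 0.700 |

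Keeping women with no change lowers power relative to dropping them. The case for retention is bias and the stated analysis set.

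**The case against.** The strongest reply is that nothing in the protocol withholds specimens from early stoppers. The Schema promises surgical tissue for every enrolled participant, the Ki-67 block is routine pathology material that exists after any hysterectomy, and 8.4 is permissive. Section 8.3 can be read as adding a closing visit after surgery without displacing the surgery-day collections. Section 7.7 has its own exception for unresolved agent-attributed events, so for those women 7.7 and 8.3 largely agree. Section 13.8 promises a check for non-random dropout and a sensitivity analysis for missing data. Exposure is 21-42 days, so few women may stop.

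Much of this stands. A reader might infer that early stoppers' tissue would be lost and that the primary result would be completers-only. The documents do not support that: it would require every early stopper to leave the study and every block to go unsent. Nor would missing blood affect the primary endpoint, which is tissue Ki-67 alone.

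The reply does not close the gap. The Schema's promise does not tell a site what to do once a woman is off study. The 7.7 exception does not cover women who stop for adherence or contraindicated medication. Section 13.8 sits under pathological response and names no method. No passage secures the pre-surgery blood and tampon after early stopping.

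**Conclusion.** The point holds as an unsecured collection and a conflict between sections. Primary tissue could be lost for treatment-related reasons. Pre-surgery estradiol, progesterone, plasma exemestane and tampon samples could be lost beyond recovery.

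With 10% stopping early, all lost, and zero to half the effect among them, the all-treated mean decrease is overstated by about 5-11% (0.19-0.38 points on 3.8). The share, the reduced effect and total loss are all assumptions. The only discontinuation figure in the documents, 6.3% for adverse events (2.2), comes from early breast cancer and does not supply a rate for this trial.

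A reader might also infer that the amendment protects power, from the fall of 0.856 to 0.821 at n = 27. It does not under the no-change assumption, where keeping the same women gives 0.786. The reason to amend is that the estimate should describe the analysis set that 13.6 names.

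**What to change.** Reconcile 7.6, 7.7, 8.3, 8.4 and 13.6, in line with the Schema's promise of tissue:

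- State in 8.3 and 8.4 that stopping exemestane, for whatever reason, ends agent but not endpoint collection. Adverse events, non-compliance, contraindicated medication and medical contraindication should not by themselves end it.
- State that, unless consent is withdrawn, every dosed woman who has the planned hysterectomy contributes the surgical tissue block and the 7.6 pre-surgery blood and tampon. Any post-surgical visit is additional.
- State in 13.6 that early stoppers stay in the primary Ki-67 analysis, subject to the existing pathology and tissue exclusions. Report how many lack a post-treatment specimen and why, and say how they are handled.

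The rules for stopping treatment are untouched. The cost is mainly amendment wording: the surgery is already planned and the collections are already study procedures.

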#### **8.4 Off-Study Criteria**

Participants may go 'off-study' for the following reasons: surgery and the final study visit has occurred, AE/SAE, lost to follow-up, non-compliance, contraindicated medication, medical contraindication, withdrawal of consent, death, determination of ineligibility (including screen failure).

#### **8.5 Study Termination**

NCI, DCP as the study sponsor has the right to discontinue the study at any time.

### **9. CORRELATIVE/SPECIAL STUDIES**

Not Applicable

### **10. SPECIMEN MANAGEMENT**

#### **10.1 Laboratories**

See lab manual for more detailed instructions.

##### **10.1.1 Tissue samples**

Endometrial biopsy tissue sample at baseline (pre-surgical) clinic visit

- First pass will immediately go into formalin and within 24 hours a Formalin Fixed Paraffin Embedded (FFPE) block will be made. Blocks will be shipped on frozen ice packs to prevent melting of the FFPE block.
- Second pass will be placed in a stabilizing agent (AllProtect) and stored at 4°C and then shipped on frozen ice packs.

Hysterectomy Tumor tissue sample at surgery

- Section snap-frozen and stored at -70/-80°C. Remove up to 1x1x1 cm of tumor and cut in half. If there is not a visible lesion, select a random 1x1x1 cm area from the endometrium. This can section can be smaller if the pathology team needs to review more of the endometrium. The amount and location of removal of specimen is at the investigators clinical discretion. This should be snap frozen and shipped on dry ice.
- A portion of the formalin fixed paraffin embedded block, which was collected as standard of care per institutional pathology guidelines, will be sent to the University of Minnesota and cut into 10 unstained 5µm slides. If the FFPE block cannot be sent due to limited amount of tumor, then 10 unstained 5µm slides will be cut and the slides will be shipped to UMN. Blocks will be shipped on ice to prevent melting of the paraffin.

Historical matched controls from repository:

- Identify a list of potential matched controls from the repository for each site that will satisfy the matching criteria mentioned in section 3 of the protocol.
- For each matched control, two samples will be collected, first from the pre-surgical biopsy remnant tissue and the second from the surgical tissue. This tissue can be sent as a block or cut into 10 unstained 5µm slides.
- All blocks or slides will be shipped at the end of study.
- If slides are sent, they should NOT be cut until the time of shipment.

Tissue analysis will be performed at the University of Minnesota (UMN) as detailed below. Specimens from the University of Wisconsin and University of Alabama will be shipped by an overnight carrier to the Biorepository laboratory at the University of Minnesota:

Biorepository & Laboratory Services  
Attn: [name]  
[name]  
[name]  
[name]  
[name]

### **10.1.2 Blood**

Clinical labs (CBC with differential, Comprehensive Metabolic Panel, FSH, estradiol, and progesterone level) will be sent to the clinical laboratories at each institution for processing.

Plasma for exemestane concentration will be shipped to:

CP Laboratory  
University of Wisconsin Hospital and Clinics  
[name]  
[name]  
[name]

### **10.1.3 Tampon**

The day before baseline (pre-surgical) clinic visit and surgery, the participant will be provided tampons for insertion. The tampon will be removed during the baseline (pre-surgical) clinic visit by the physician at the time of the pelvic exam and during surgery.

## 10.2 Collection and Handling Procedures

The UWCCC CP Laboratory will prepare sample kits for each subject enrolled on the study, which will include tampons, endometrial pipelles and two 6mL green top tubes for collecting the pharmacokinetic samples.

**10.2.1 Vaginal Tampon (baseline (pre-surgical) clinic visit and day of surgery)** - Tampons will be collected in the clinic or operating room and immediately will be placed into a 50 mL conical polypropylene tube with a screw-top lid into which 30 mL of cold, sterile phosphate buffer saline (PBS) will be added. The tampon can soak in the cold PBS solution for up to 12 hours before agitation. The tube will be mounted on a platform rocker for 30 minutes at 4°C for gentle agitation. The tampon will be carefully removed from the conical tube and inserted into a 35cc syringe. The plunger of the syringe will be slowly depressed to completely compress the tampon, thereby releasing cells and any of the remaining PBS solution from the tampon. The tampon will then be discarded. The PBS solution that was in the initial conical tube with the tampon should be combined with the PBS solution that was compressed out of the tampon to yield approximately 30 mL. This 30 mL cell suspension will then be equally divided into two 50 mL conical polypropylene tubes and centrifuged for 10 minutes to pellet the cells. Remove 14 mL of supernatant from both of the conical tubes by gently pipetting and combine into one 50 mL conical polypropylene tube. The cell pellets will be re-suspended in the remaining 1 mL of PBS using a disposable glass pipet and transferred to 1.5 mL Eppendorf tubes each and spun for 10 minutes at 3000xg. After separating the cell pellets the remaining 1 mL of supernatant from both tubes will be combined with the supernatant in the 50 mL conical polypropylene tube. The supernatant and two cell pellets that remain at the bottom of the two 1.5 mL Eppendorf tubes will be stored at -70/ -80°C until it is sent to the UMN for analysis after the surgical tampon is collected at the below mentioned address.

Biorepository & Laboratory Services  
Attn: [name]  
[name]  
[name]  
[name]  
[name]

**10.2.2 Tumor biopsy specimens (baseline (pre-surgical) clinic visit)** - At the baseline (pre-surgical) clinic visit, participants will undergo an endometrial biopsy in clinic to ensure adequate tissue for IHC and genetic analysis as well as to confirm pathology. All biopsy samples will be sent to the UMN for proteomics, DNA analysis, central pathology review, and IHC. This biopsy will be done for research purposes only and is routinely performed during a pelvic/speculum exam in gynecologic oncology clinics without additional anesthesia, sedation or monitoring. Two biopsy “passes” with an endometrial pipelle will be performed. The first will be formalin-fixed, paraffin embedded (FFPE), and sent to UMN for central pathology review and IHC analysis. The first pass will be made into formalin and within 24 hours a Formalin Fixed Paraffin Embedded (FFPE) block will be made. Blocks will be shipped on ice to UMN for central pathology review and IHC analysis. The second pass will be placed in a stabilizing agent (AllProtect) stored at 4 °C and then shipped on frozen ice packs.

**10.2.3 Surgical Samples** - The surgical pathologic specimen (the uterus) will be processed as is the usual standard at each institution. A portion of the FFPE tumor block will be collected and batch shipped to UMN

to be cut into 10 unstained 5 $\mu$ m slides. If the FFPE block cannot be sent due to limited amount of tumor, then 10 unstained 5 $\mu$ m slides will be cut and the slides will be shipped to UMN. Blocks and slides will be shipped on frozen ice packs to prevent melting of the paraffin. An additional section of the tumor (up to 1x1x1 cm) will be collected, cut in half and snap frozen to -70/-80°C for genetic sequencing. If there is not a visible lesion, select a random 1x1x1 cm area from the endometrium. This section can be smaller if the pathology team needs to review more of the endometrium. The amount and location of the sample is at the investigators clinical discretion. This tumor section will also be batch shipped to UMN on dry ice.

**10.2.4 Research Blood Samples** - At each pharmacokinetic time point (baseline and Day 22-43 (Day of surgery - drawn before the surgery), blood will be drawn to fill one 6mL heparinized tube. The tubes will be centrifuged for 10 minutes at 4°C to separate plasma. The plasma will be divided into 2 cryovial tubes. The 2 cryovial tubes will be labeled with the labels provided in the kit. The participants' number, initials, and date of processing will be added to the labels. The cryovial tubes will be frozen at -70/-80°C, and save for transport to the UWCCC CP Laboratory.

